5.4.7 Glasdegib specific dose adjustments

In the event of significant toxicity, dosing must be interrupted, delayed and/or reduced as outlined below. In the event of multiple toxicities, dose modification should be based on the worst toxicity observed. Patients must be instructed to notify investigators at the first occurrence of any adverse symptom/s.

Dose modifications may occur in three ways:

- Within a cycle: Dosing interruption until adequate recovery followed by dose reduction (if required) of glasdegib during a given treatment cycle.
- Between cycles: The next treatment cycle may be delayed if toxicity from the preceding cycle persists.
- In the next cycle: Dose reduction may be required based on toxicities experienced in the previous cycle.

Dosing Interruptions for glasdegib

Patients experiencing Grade 3 or 4 toxicities potentially attributable to glasdegib should have their glasdegib treatment interrupted regardless of when it occurs in the cycle until the toxicity resolves or returns to baseline or </= grade 1.

Appropriate follow-up assessments should be implemented until adequate recovery (toxicity resolves or returns to baseline or </= grade 1) occurs. The criteria that must be met prior to resuming treatment with glasdegib are described below.

Depending on when the adverse event resolved, treatment interruption may lead to the patient missing all subsequent planned doses of glasdegib within the cycle. If the AE leading to treatment interruption recovers within the same cycle, re-commencement of dosing in that cycle is allowed. Glasdegib doses omitted for toxicity will not be replaced within that cycle (e.g., cycles will not be prolonged beyond the 28 days in order to make up for any missed glasdegib doses during that cycle).

The need for a dose reduction at the time of treatment resumption should be based on the criteria outlined below, unless specifically agreed otherwise following discussion between the treating physician and the PI. If a dose reduction for glasdegib is applied in the same cycle, the patient must return to the clinic to receive a new supply of drug.

In the event of glasdegib treatment interruption for reasons other than treatment-related toxicity (e.g., elective surgery) for a duration >21 days, the details of treatment resumption will be determined in consultation with the PI.

Glasdegib treatment should be interrupted for ANC <100/mm³ and /or platelets <10,000/mm³ regardless of when it occurs.

Re-commencement of treatment with glasdegib may not occur until the recovery parameters described in Table 6 below are met.

Patients who are experiencing ongoing dose delays >8 weeks due to unresolved grade ≥ 3 adverse events should be taken off treatment.

At the time of glasdegib re-initiation the non-hematologic toxicities listed in Table 7 below have returned to baseline or ≤ Grade 1 severity.

If these conditions are met within ≤21 days of dose interruption, glasdegib may be resumed. If these parameters have not been met following >21 days of dose interruption, permanent discontinuation of treatment with glasdegib should be considered.

QTcF Interval Monitoring and Management: Patients should be closely monitored for potential cardiovascular symptoms. Appropriate monitoring should include clinical examinations, vital signs, routine ECGs, and AE monitoring. In case of QTcF prolongation, concomitant conditions such as electrolyte imbalances, hypoxia, or use of medications affecting the QT interval should be ruled out or corrected. In case of clinically significant toxicities, glasdegib administration should be interrupted and the dose reduced as indicated in Table 8 below (Glasdegib Dose Modifications for mean QTcF (mQTcF) Prolongation).

Concomitant administration of glasdegib with moderate/strong CYP3A4/5 inhibitors and drugs with known risk of Torsade de Pointes (TdP) is not recommended due to the potential for drug-drug interaction to prolong the QTcF interval. However, if it is medically necessary for patients to use these medications please refer to Section below for details on required assessments and monitoring procedures.

Investigators must be aware of the QTcF-prolonging potential of all medications that patients on study at their site are taking, and should take appropriate action when clinically indicated. Given the potential for QTcF prolongation, the measurement and immediate correction of electrolyte abnormalities such as potassium and magnesium and of other reversible causes of QTcF prolongation such as hypoxia, are especially important during the study. In the event that the QTcF interval is prolonged beyond 480 ms (CTCAE v.4.03 Grade≥ 2), the protocol glasdegib Dose Modifications for mean QTcF (mQTcF) Prolongation must be referenced and actioned (Table 9). Throughout the study additional ECG and cardiac consultation should be obtained as clinically indicated.

Dose Reductions for glasdegib

Following dosing interruption or cycle delay due to toxicity, the glasdegib dose may need to be reduced when treatment is resumed.

Dose reduction of glasdegib by 1 or if necessary, 2 dose levels will be allowed depending on the type and severity of toxicity encountered. In the specific situations where clinical benefit is observed, glasdegib can be reduced below 50 mg QD upon PI approval. All dose modifications/adjustments must be clearly documented in the patient's notes and CRF.

Table 5: Glasdegib dose reduction schema

Glasdegib dose (mg Qday)
100
75
50
25*

*Note: If clinical benefit is observed, glasdegib may be reduced below 50 mg Qday

following PI approval.

Table 6. Glasdegib dose modification for hematologic toxicities

Toxicity (Platelets and Neutrophils only)	Glasdegib (PF-04449913)³
Recovery within 14 days from when the next cycle is due to start (corresponding to recovery before or on Day 42 of the current cycle) ^{1,2}	No Change
Recovery within 14 days, but within 21 days from when the next cycle is due to start (corresponding to recovery before or on Day 42 and before or on Day 49 of the current cycle) ^{1,2}	First episode: decrease by 1 dose level Second episode: decrease by 1 dose level Third episode: permanently discontinue
No recovery by Day 49 of the current cycle	Permanently discontinue

¹For patients without reduced baseline counts (defined as ANC \geq 1,000/mm 3 and platelets \geq 50,000/mm 3 prior to the first cycle): Recovery is defined as ANC $>$ 500/mm 3 and platelets $>$ 20,000/mm 3

² For patients with reduced baseline counts (defined as ANC \geq 1,000/mm 3 OR platelets \geq 50,000/mm 3 prior to the first cycle): Recovery is defined as: reaching at least 50% of cell line(s) counts (where hematological toxicities were observed) of the previous cycle, e.g., if ANC when starting the previous cycle was 800/mm 3 , ANC recovery is defined as ANC \geq 400/mm 3

³ Glasdegib (PF-04449913) treatment should be interrupted for ANC $<$ 100/mm 3 and/or platelets $<$ 10,000/mm 3 regardless of when it occurs

Table 7. Glasdegib dose modification for non-hematologic toxicities

Toxicity (NCI CTCAE version 4.03)	Glasdegib (PF-04449913)
Renal Toxicity	First episode: decrease by 1 dose level Second episode: decrease by 1 dose level Third episode: permanently discontinue
\geq Grade 3 toxicity (Nausea, vomiting, and/or diarrhea must persist at \geq Grade 3 (despite maximal appropriate medical therapy) to require dose modification)	First episode: decrease by 1 dose level Second episode: decrease by 1 dose level Third episode: permanently discontinue

Table 8. Glasdegib Toxicity Grading for QTcF Prolongation

CTCAE v 4.03	Grade 1	Grade 2	Grade 3 ^{**}	Grade 4
Electrocardiogram QT corrected (QTc) interval prolonged *	450-480msec	481-500msec	≥501 msec at least two separate ECGs	QTc ≥501 or >60 msec from change from baseline and Torsade de pointes or polymorphic ventricular tachycardia or signs/symptoms of serious arrhythmia

* The severity of QTc prolongation assessment is to be done by calculating a mean QT of 3 consecutive ECGs performed approximately 2 minutes (but no longer than 5 minutes) apart by using the Fridericia correction method (mQTcF).
** If mQTcF is ≥501 msec continuous ECG monitoring and cardiology consultation are required.

Table 9: Evaluation and management of QTcF changes with Glasdegib therapy

Category	Requirement	Grade			
		1	2	3	4
ECG monitoring	Continuous ECG monitoring and cardiology consultation for mQTcF \geq 501 msec			x	x
Initial PF 04449913/ placebo action	Discontinue and do not re-challenge.				x
	Interrupt treatment		x	x	
	Continue at same level	x			
General management	Assess for and correct electrolyte abnormalities.	x	x	x	x
	Withhold any concomitant medications if possible that may cause QTc prolongation.		x	x	x
Resume PF 04449913/placebo dosing	At prior dose if mQTcF returns to \leq 470 msec and to within 20 msec of baseline in 7 days and if no prior dose interruption related to mQTcF prolongation has occurred		x	x	
	At one lower dose level if mQTcF returns to \leq 470 msec and to within 20 msec of baseline between 7-14 days, and if no prior dose interruption related to mQTcF prolongation has occurred		x	x	
	At one lower dose level if mQTcF returns to \leq 470 msec and to within 20 msec of baseline in 14 days if one prior dosing interruption related to mQTcF prolongation has occurred		x		
Management after dose resumed	An ECG should be repeated and mQTcF re-assessed approximately 7 days after PF-04449913/placebo dosing resumption following interruption for a mQTcF prolongation		x	x	
Discontinue PF-04449913/placebo permanently	The mQTcF prolongation does not return to \leq 470 msec and to within 20 msec of baseline after 14 days		x	x	
	The Grade \geq 2 mQTcF prolongation recurs after one dose reduction related to mQTcF prolongation		x	x	
	The Grade \geq 3 mQTcF prolongation recurs after one prior dosing interruption related to mQTcF prolongation has occurred			x	
	If at any time during the 14 day window that PF 04449913/placebo is stopped due to QTcF prolongation the patient has a confirmed mean QTcF interval $>$ 515 msec or becomes symptomatic		x	x	

Table 10
Dose Modifications for PF-04449913/placebo in Case of Drug Class Related AEs

Muscle Spasms or Myalgia	Grade 1	Grade 2	Grade 3
PF-04449913/ Placebo	
Continue at same dose level.
 
Administer oral rehydration solutions containing electrolytes.^a
 
Consider other appropriate interventions (eg, anti-spasmodics) as per institutional guidelines.
 
Evaluate levels of: CK, Vit B6, Vit D, ferritin, transferin and electrolytes (Na, K, Mg, Ca and P).^b
 
If CK is elevated, evaluate urine and serum myoglobin, CK isoenzymes, and plasma creatinine.
	
Continue at same dose level.
 
Administer oral rehydration salts containing electrolytes.^a
 
Consider other appropriate interventions (eg, anti-spasmodics) as per institutional guidelines.
 
Evaluate levels of: CK, Vit B6, Vit D, ferritin, transferin and electrolytes (Na, K, Mg, Ca and P).^b
 
If CK is elevated, evaluate urine and serum myoglobin, CK isoenzymes, and plasma creatinine.
 
If event persists, hold dose until resolution to Grade ≤ 1.
 
Upon resolution, restart at prior dose, or for prolonged muscle spasms, consider reducing dose by one dose level.
	
Hold dose.
 
Administer oral re-hydration salts containing electrolytes.^a
 
Consider other appropriate interventions (eg, anti-spasmodics) as per institutional guidelines.
 
Evaluate levels of: CK, Vit B6, Vit D, ferritin, transferin and electrolytes (Na, K, Mg, Ca and P).^b
 
If CK is elevated, evaluate urine and serum myoglobin, CK isoenzymes, and plasma creatinine.
 
Upon resolution to Grade ≤ 1, restart study treatment at next lower dose level.
 
If the event does not resolve within 3 weeks to Grade ≤ 1, at the discretion of the Investigator the dose may be restarted at the next lower dose level or the patient may be permanently discontinued from study treatment.

In the event of alopecia or dysgeusia, investigator discretion should be applied with respect to dose interruption and/or dose reduction of PF-04449913 as preliminary analysis of available clinical data suggests that these events are not dose dependent.

CYP3A4/5 Inducers: Glasdegib (PF-04449913) metabolism may be induced when taking CYP3A4/5 inducers, resulting in reduced plasma concentrations. The impact of CYP3A4/5 inducers on PF-04449913 pharmacokinetics has not been studied in the clinic. Therefore co-administration of PF-04449913 with any of the following and other moderate/strong CYP3A4/5 inducers is not permitted from study entry until study treatment discontinuation (avasimibe, mitotane, phenytoin, enzalutamide, semagacestat, bosentan, genistein, thioradazine, naftcillin, modafinil, carbamazepine, phenobarbital,

phenytoin, rifampin, rifabutin, rifapentine, St. John's Wort). A comprehensive list of strong CYP3A4/5 inducers is provided in the Appendix.

Selection of concomitant medication with no or minimal **CYP3A4/5 inhibition** potential is recommended. Moderate/strong CYP3A4/5 inhibitors should be used with caution and only if considered medically necessary. If a moderate/strong CYP3A4/5 inhibitor is to be initiated in addition to glasdegib the guidance provided below requiring additional ECG monitoring before, during and after starting the medication, electrolyte monitoring (including correction and re-checking values) and dose modifications for QT prolongation must be followed.

The concomitant administration of glasdegib and drugs with a known risk of Torsade de pointes should be avoided whenever possible. A list of such drugs is provided in the Appendix. Use of these drugs is not recommended unless there are no alternatives. If a TdP drug is to be initiated in addition to glasdegib the guidance provided below requiring additional ECG monitoring before, during and after starting the medication, electrolyte monitoring (including correction and re-checking values) and dose modifications for QT prolongation must be followed.

QT prolonging medications (without a risk of TdP) should be avoided whenever possible. Concomitant administration of multiple moderate/strong CYP3A4/5 inhibitors, TdP drugs, and/or QT prolonging medications (without a risk of TdP) is not recommended and must be discussed with the PI.

The acceptable mean on-treatment upper limit of QTcF interval is 480 msec. If any patient has a mean pre- or post-dose QTcF value >480 msec, please refer to Table **'Dose Modifications for mean QTcF (mQTcF) Prolongation' (Table 9)** for detailed instructions on management of QTcF prolongation and handling dose delays and dose modifications for glasdegib.

If a moderate/strong CYP3A4/5 inhibitor or TdP drug will be initiated in addition to Glasdegib (PF-04449913) the following guidance must be followed:

-Prior to the start of a moderate/strong CYP3A4/5 inhibitor or TdP drug:
ECGs pre-glasdegib dose, 1 and 4 hours post-glasdegib dose;
Follow dose modifications for QT prolongation.

-After starting a moderate/strong CYP3A4/5 inhibitor or TdP drug: ECGs on Day 2 or 3 and on Day 5, 6, or 7:

-Perform additional ECG testing as appropriate;

- Perform routine electrolyte monitoring (Ca, K, Cl, Mg), implement timely electrolyte correction, followed by appropriate re-checking of values.

When there is an urgent need to start a moderate/strong CYP3A4/5 inhibitor or TdP drug, administration of these medications should not be delayed, the Investigator should consider temporarily interrupting glasdegib dosing and should implement these additional monitoring procedures as soon as it is reasonably possible.

5.4.7 Modifications of dose schedules other than the above will be allowed within the following guidelines:

5.4.7.1 Dose adjustments by more than 1 dose level at a time for azacitidine, venetoclax or glasdegib (e.g., from azacitidine 75 mg/m² to 25 mg/m²) can be considered when judged in the best interest of the patient (e.g. severe myelosuppression) when toxicity has resolved. The reason for this reduction will be discussed with the PI or Co-PI and documented in the medical record.

5.4.7.2 A patient who has had a dose reduction because of any of the reasons mentioned above may have their dose escalated provided the patient has remained free of toxicity requiring dose adjustments as defined above for at least 1 month. Escalation will be made by 1 dose-level increment only, and not more frequent than every month. The dose of any agent must not exceed the RP2D dose for that agent in this protocol (i.e. azacytidine dose cannot exceed 75mg/m² x 7 days, venetoclax dose cannot exceed 400 mg/day, and glasdegib dose cannot exceed 100 mg/day).

5.4.7.3 Treatment interruptions and dose modifications other than the ones mentioned above can be considered after discussion with the PI and proper documentation of the rationale. Dose adjustment/delay of only one of the agents is permissible if the toxicity is most likely judged to be related to one of the agents by the investigator (e.g., in patients with autoimmune thyroiditis or autoimmune hepatitis this would be likely secondary to avelumab or PF-04518600, in patients with cytopenias this would be likely secondary to azacitidine and venetoclax, in patients with hepatic congestion or transaminitis this may be secondary to the GO).

5.4.8 Duration of Therapy

In the absence of treatment delays due to adverse events, treatment may continue until one of the following criteria applies:

1. Clinically significant progressive disease, or
2. Intercurrent illness that prevents further administration of either treatment agent, or
3. Patient request, or
4. General or specific changes in the patient's condition render the patient unacceptable for further treatment in the judgment of the investigator, or
5. Unacceptable toxicity that in the opinion of the investigator makes it unsafe to continue therapy.

It is planned that up to a total of 24 cycles of therapy will be administered for patients deriving benefit from this regimen. Continuation of therapy for patients completing 24 cycles of therapy may be considered on a case- by-case basis after discussion with the principal investigator and IND Office.

All patients receiving at least one dose of any of the two/three drugs to be received in the combination will be considered evaluable for toxicity and efficacy by intent-to-treat analysis.

5.5 Supportive Care:

Management Algorithms for Treatment of immuno-oncology agents Related

Adverse Events Immuno-oncology (I-O) agents are associated with AEs that can differ in severity and duration than AEs caused by other therapeutic classes. Avelumab and PF-04518600 are considered an immuno-oncology agent in this protocol. Early recognition and management of AEs associated with immuno-oncology agents may mitigate severe toxicity. These IO-agent/s has a known safety profile however, a general principle is that differential diagnoses should be diligently evaluated according to standard medical practice. Non- inflammatory etiologies should be considered and appropriately treated. Corticosteroids are a primary therapy for immuno-oncology drug-related adverse events, and avelumab is no exception. The oral equivalent of the recommended IV doses may be considered for ambulatory patients with low-grade toxicities. The lower bioavailability of oral corticosteroids should be taken into account when switching to the equivalent dose of oral corticosteroids. In cases with slightest suspicion of IO-toxicities it is encouraged that the treating physician consult the PI/Co-PI or immunotherapy expert in the department as soon as possible.

Management Algorithms have been developed to assist investigators in assessing and managing the following groups of adverse events: Endocrinopathies, Gastrointestinal, Hepatic, Neurological Pulmonary, Renal and Skin. These algorithms are found in the “Avelumab and PF-04518600 Investigator Brochures” (Appendix) and “Table 4- Management of immune related adverse events” of this protocol. The guidance provided in these algorithms should not replace the Investigator’s medical judgment but should complement it.

Finally, consultation with a medical or surgical specialist, especially prior to an invasive diagnostic or therapeutic procedure, is highly recommended.

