Evaluation of the first 6 patients in each treatment arm will occur after all patients have completed two cycles of treatment (or at least 56 days from the first day of treatment). Enrollment will be halted while the first 6 patients in each treatment arm are evaluated for safety. The treatment combination will be considered as safe, and continue to enroll to a total of 21 patients (Arms E-F) or 24 patients (Arms C-D) or 30 patients (Arm B) when there are no more than 1 out of 6 patients with DLTs in the first cycle of treatment. If any patients in the first 6 of each treatment arm withdraw from the study without a DLT event prior to completing the first cycle of treatment, they will be replaced for the assessment of DLT rate. This will allow for early identification of significant toxicities and early stoppage in potentially toxic arms. If 2 or more out of 6 patients have DLTs in the first cycle of treatment in any arm, then an additional 6 patients will enroll at a next lower dose level to be determined by the PI, sponsor (MDACC IND office), and Pfizer team after reviewing the safety, efficacy, and PD data from the first 6 patients enrolled. If no more than 1 out of the additional 6 patients treated with the lower dose level experience DLTs, this treatment combination will be considered as safe and continue to enroll to a total of 21 patients (Arms E-F) or 24 patients (Arms C-D) or 30 patients (Arm B). If 2 or more out of these 6 additional patients experienced DLTs, then this arm will be halted.

The Investigator is responsible for completing the cohort summary template and submitting to the IND office Medical Monitor for review and approval prior to continuing accrual beyond each set of 6 patients in each arm of the study. A copy of the cohort summary should be placed in the Investigator's Regulatory Binder under "sponsor correspondence". This should be submitted after the first six patients.

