3.4 DLT Definition

DLT is defined as clinically significant non-hematologic adverse event or abnormal laboratory value assessed as unrelated to disease progression, intercurrent illness, or concomitant medications and occurring during the first cycle (28 days) on study that meets any of the following criteria:

- CTCAE Grade 3 AST (SGOT) or ALT (SGPT) for $>/= 7$ days or grade 3 hyperbilirubinemia for $>/= 7$ days

- CTCAE Grade 3 AST (SGOT) or ALT (SGPT) accompanied by grade 2 bilirubin increase
- CTCAE Grade 4 AST (SGOT) or ALT (SGPT) of any duration
- All other clinically significant non-hematological adverse event that is Grade 3 or 4 according to the NCI common terminology criteria version 4.0 with the following exceptions:
 - Grade 3 or 4 nausea, vomiting and diarrhea will be considered DLT only if not controlled by optimal therapy within 72 hours.
 - Grade 3 biochemical abnormalities (e.g., lipase or bilirubin elevation) will only be considered DLT if accompanied by clinical consequences. Grade 3 or 4 electrolyte abnormalities will only be considered DLT if possibly related to study drug and not corrected by optimal replacement therapy within 72 hours.
- Results in discontinuation of therapy
- Any treatment-related death;

Grade 4 neutopenia lasting \geq 42 days from start of cycle in absence of evidence of active AML.

For patients in venetoclax-containing arms (i.e. Arms B and D) who do not receive venetoclax on day 1 due to logistical and/or financial reasons, the DLT period will be extended to 28 days from the first dose of venetoclax. For evaluation of neutropenia-related DLT, the DLT period will be 42 days from the first dose of venetoclax. Evaluation of the first 6 patients in each of the venetoclax containing treatment arms (arms B and D) will occur after all patients have completed two cycles of treatment (or at least 56 days from the first dose of venetoclax). Enrollment will be halted while the first 6 patients in each of these treatment arms are evaluated for safety.

Please see statistics section (section 11.0) for efficacy and toxicity stopping rules to be applied independently to each cohort.

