- One cycle of therapy is defined as 28 days (+/- 4 days) or 4 weeks. Patients will receive one cycle of therapy every 28 days (+/- 4 days). During the DLT evaluation period the cycle must be a minimum 28 days.

(B) Arm B (Azacitidine + venetoclax + GO in RR AML): N= Up to 26

- Azacitidine will be administered subcutaneously (SQ) or intravenously (IV) for the first 7 days of every cycle with daily schedule of 7 consecutive days (Days 1-7) or for days 5-2-2 which is 5 consecutive weekdays (Days 1-5) with rest on the 2 weekend days (Days 6 and 7) and then dosing the first two weekdays of the next week (Days 8 and 9) of each 28-day cycle (+/- 4 days) as determined by treating physician. Both SQ and IV forms of administration are FDA approved and considered interchangeable. Patients may start receiving azacitidine by one route and changed to the other, and also administration schedules from one schedule and changed to the other at any time as needed based on patient and/or physician preference.

- Venetoclax will be given orally on days 1-28 of cycle 1 and days 1-21 of subsequent cycles. During cycle 1, venetoclax will be dose escalated daily to the goal dose of 400mg daily. Patients will receive 100mg on day 1, 200mg on day 2 and 400mg on day 3 and onwards. This dosing applies to patients in both Phase I and II components of this study.

To minimize the risk of tumor lysis syndrome (TLS), All patients will be hospitalized for the entirety of the venetoclax dose escalation starting at least on day -1 of treatment initiation and until 24 hours after the completion of venetoclax dose escalation. To mitigate the risk for TLS, subjects must be receiving tumor lysis prophylaxis, including hydration (oral, intravenous) and treatment with a uric acid reducing agent (allopurinol, rasburicase) prior to and during the venetoclax ramp up period of Cycle 1. Physicians should leukoreduce with hydroxyurea to reduce the peripheral white blood count to below 15,000/ μ L prior to the administration of the first dose of venetoclax. If the WBC is $>15,000/\mu$ L the venetoclax should not be initiated till the white count is brought down to below 15,000/ μ L

As venetoclax is obtained commercially, some patients may have delays in beginning venetoclax due to financial or other logistical considerations. Even if venetoclax is not yet available, patients may begin azacitidine on day 1.

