The dose of GO should be held if total bilirubin $> 2 \times$ ULN or if AST or ALT $> 2.5 \times$ ULN. If laboratory studies return to acceptable range, then the dose of GO may be made up later in the cycle at the discretion of the treating physician after consultation with the PI.

- Following completion of the infusions, it is recommended to be observed for 2 hours post-infusion for potential infusion-related reactions. The ambulatory treatment center/inpatient nurse will use the institutional flowsheet to document observation of the patient as per institutional standards.

(C) Arm C (Azacitidine + avelumab + GO in RR AML): N= Up to 26

- Azacitidine will be administered subcutaneously (SQ) or intravenously (IV) for the first 7 days of every cycle with daily schedule of 7 consecutive days (Days 1-7) or for days 5-2-2 which is 5 consecutive weekdays (Days 1-5) with rest on the 2 weekend days (Days 6 and 7) and then dosing the first two weekdays of the next week (Days 8 and 9) of each 28-day cycle (+/- 4 days) as determined by treating physician. Both SQ and IV forms of administration are FDA approved and considered interchangeable. Patients may start receiving azacitidine by one route and changed to the other, and also administration schedules from one schedule and changed to the other at any time as needed based on patient and/or physician preference.
- Avelumab infusion at a dose of 10 mg/kg (maximum dose: 2000 mg) should begin 30-60 minutes after the completion of azacitidine on day 1, as described above, whenever possible. A second dose of avelumab will be administered on Day 14 of each 28 day cycle. Premedication with an antihistamine and with paracetamol (acetaminophen) (for example, 25-50 mg diphenhydramine and 500-650 mg paracetamol [acetaminophen] IV or oral equivalent) is mandatory and recommended to be given approximately 30 to 60 minutes prior to each dose of avelumab. This regimen may be modified based on local treatment standards and guidelines as appropriate provided it does not include systemic corticosteroids.

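### In Arms B-F, lead-in replacement depends on withdrawal and not on exposure to every component, and DLT-evaluable is never defined

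*Combined protocol and SAP*

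**What the plan says.** **Decision rule.** Section 3.3, repeated in Section 11, lets an arm in B-F continue "when there are no more than 1 out of 6 patients with DLTs in the first cycle of treatment".

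**Replacement.** The same sections say that any of the first six who "withdraw from the study without a DLT event prior to completing the first cycle of treatment, they will be replaced" for the DLT rate. No other trigger is given. The sentence names the first six only. It does not mention the additional six at a lower dose level or the later looks every three patients.

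**Evaluability.** Section 5.2 counts the first six evaluable subjects and then every three, without defining the term for DLT. Section 5.4.8 says that anyone "receiving at least one dose of any of the two/three drugs to be received in the combination will be considered evaluable for toxicity"; the sentence is worded as an intent-to-treat rule that covers efficacy too. The Statistical Analysis Plan part of Section 11 has a similar any-dose set. For Arm A, Section 5.2 provides separately that patients who cannot be assessed for DLT are replaced. Arms B-F have no such sentence.

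**Foreseeable gaps in exposure.**
- Section 5.2 (Arm B) expects that "some patients may have delays in beginning venetoclax due to financial or other logistical considerations". Venetoclax is also not started while the white count exceeds 15,000/µL.
- In Arms B and C, GO is one dose on Day 8. "The dose of GO should be held if total bilirubin" or transaminases exceed stated limits, and making it up later in the cycle is discretionary.
- Section 5.3 allows the other drugs to continue when one is stopped for safety.

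**What is covered.** For a late venetoclax start in Arms B and D, Section 3.4 says "the DLT period will be extended to 28 days from the first dose of venetoclax".

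**The concern.** The lead-in exists to confirm that the combination is tolerable. A patient who completes cycle 1 without one component says little about the combination, yet still fills one of six places. With a limit of one DLT in six, each such place pushes the count towards clearance.

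The protocol's own limits make the GO case foreseeable. Section 4.1.5 admits AST or ALT up to 5 x ULN when judged leukemia-related. Section 5.2 holds GO above 2.5 x ULN. A patient can therefore enter already meeting the hold condition, remain on study, and never trigger replacement.

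At stake is the decision that opens an arm to 24 patients (C-D) or 30 (B).

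**Working it through.** **1. Reproduce the plan's toxicity figures.** Section 11 gives the prior Beta(0.3, 1.7) and stops an arm if Pr(P_T > 0.15 | data) > 0.80. The smallest r for which Beta(0.3 + r, 1.7 + n - r) meets this is 2, 3, 4, 4, 5, 5 at n = 6, 9, 12, 15, 18, 21. These match the Arm B boundaries exactly. An exact binomial recursion over the looks agrees with the published stopping probabilities to within 0.013:

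| Arm | True DLT rate | Plan | Recomputed |
|---|---|---|---|
| B | 0.15 | 0.342 | 0.345 |
| B | 0.30 | 0.856 | 0.864 |
| C-D | 0.15 | 0.290 | 0.302 |
| E-F | 0.15 | 0.264 | 0.259 |

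The published figures therefore treat every counted patient as at the full DLT rate.

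**2. Lead-in with all six fully exposed.** P(at most 1 of 6) = (1-p)^6 + 6p(1-p)^5.
- p = 0.30: 0.1176 + 0.3025 = 0.420
- p = 0.40: 0.0467 + 0.1866 = 0.233

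**3. Lead-in with m incompletely exposed patients.** Their number m and their DLT rate q are assumptions, because the documents give neither. At p = 0.30:
- m = 1: (1-q)[0.7^5 + 5(0.3)(0.7^4)] + q(0.7^5) = 0.5282(1-q) + 0.1681q. This is 0.528 at q = 0 and 0.492 at q = 0.10.
- m = 2: (1-q)^2[0.7^4 + 4(0.3)(0.7^3)] + 2q(1-q)(0.7^4) = 0.6517(1-q)^2 + 0.4802q(1-q). This is 0.652 at q = 0 and 0.571 at q = 0.10.

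| Triplet DLT rate | m = 0 | m = 1, q = 0.10 to 0 | m = 2, q = 0.10 to 0 |
|---|---|---|---|
| 0.30 | 0.420 | 0.492 to 0.528 | 0.571 to 0.652 |
| 0.40 | 0.233 | 0.311 to 0.337 | 0.408 to 0.475 |

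**4. Effect after the later looks.** Take the lead-in six as the first toxicity look, q = 0.05, and later patients fully exposed. Apply the published boundaries at each later look. The probability of no early toxicity stop is:

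| Arm | Triplet DLT rate | m = 0 | m = 1 |
|---|---|---|---|
| B | 0.30 | 0.14 | 0.17 |
| B | 0.40 | 0.02 | 0.03 |
| C-D | 0.30 | 0.22 | 0.27 |
| C-D | 0.40 | 0.06 | 0.09 |

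With two such patients, the Arm B figure at 0.30 is 0.21. Incomplete exposure among later patients would raise these values and is not modelled.

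**The case against.** A reader might infer that anyone given one dose of one drug counts in the lead-in and is never replaced. The documents do not support that. Section 5.4.8 is worded as an intent-to-treat set for toxicity and efficacy, and nothing ties it to the six-patient decision. Sections 3.3 and 11 say that those who leave without a DLT "prior to completing the first cycle of treatment, they will be replaced for the assessment of DLT rate". A late venetoclax start moves the DLT window. This part of the objection stands and limits the point to patients who stay on study.

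It can also be said that a patient who never starts venetoclax has a DLT window that never opens, and so should not count. That is a sensible reading, but the plan does not state it. Section 5.2 allows the review once two cycles have been given, and no sentence removes or replaces this patient. GO has no counterpart to the venetoclax provision.

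Section 2.8 reports no DLTs among 3 evaluable patients of 5 treated in Arm F, so any-dose counting was apparently not used there. That passage speaks of response evaluability, and its criterion for DLT is unwritten. It shows that a definition is needed.

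The held-GO route is narrow: a dose can be made up, most patients should enter below the hold limits, and later liver abnormalities may themselves be DLTs. The Medical Monitor must also approve a cohort summary before accrual continues. These points lower the likely frequency, but they do not supply a rule.

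**Conclusion.** The point holds as a missing definition with a predictable direction of bias. For a patient who remains on study through cycle 1 without one component, the stated rule gives no replacement, and the DLT count can include that patient as event-free.

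At an assumed 30% DLT rate with the triplet and 0-10% without the third drug, one such patient moves the chance of clearing the lead-in from 0.42 to 0.49-0.53, and two move it to 0.57-0.65. How many such patients would occur is unknown.

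A reader might take these as probabilities of a toxic triplet reaching full enrolment. They are not. Once the three-patient looks are applied, with a 5% rate without the third drug, one such patient moves the chance of no early toxicity stop at 30% from 0.14 to 0.17 in Arm B and from 0.22 to 0.27 in Arms C-D. The change should be made because the decision rests on six patients and the remedy is cheap.

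**What to change.** - Keep the any-dose set in Section 5.4.8 and the Statistical Analysis Plan for the overall safety and intent-to-treat summaries, and state that it does not govern DLT decisions.
- In Sections 3.3 and 11, define DLT-evaluable for Arms B-F as a patient who had a DLT, or who received at least one dose of every assigned component in cycle 1 and was followed for the full DLT period, including the venetoclax-based period in Section 3.4.
- Replace all others for the first-six and additional-six decisions, whether the cause is withdrawal, a missed component, or death or removal without a DLT. Use the same set for the three-patient toxicity looks.
- List replaced patients and the reason in the cohort summary, so that a component missed because of toxicity short of a DLT stays visible.
- Reconcile Sections 2.8, 3.3, 3.4, 5.2, 5.4.8 and 11 so that evaluable has one meaning for DLT.

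The cost is protocol and SAP wording, and possibly one or two replacement patients per lead-in within the arm maximum, with the wait to enrol and follow them. No dose, eligibility limit or hold rule changes.
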